2.3.2 Known Potential Benefits

Participants are not expected to benefit from the study directly, as they will not be receiving new interventions not otherwise available to them in the ED. We expect that overdose education and provision of naloxone (in both conditions) will reduce future opioid-related adverse events among patients presenting with nonfatal OD; of note, OEND is generally standard care at study sites already, but for the study we will ensure it occurs for all study participants. The Relay peer navigator intervention has the potential to provide additional benefit to patients, but its effectiveness has not been established. The community at large, including patients and providers, stands to benefit from the knowledge gained from this study about reducing OD fatalities, and barriers and facilitators to OD prevention programs. The results of this study are critical to advancing science around preventing OD fatalities, informing the allocation of resources in NYC, and informing other jurisdictions as they scale up opioid OD prevention efforts.

CONFIDENTIAL

This material is the property of the NYU School of Medicine and NYU Langone Health. Do not disclose or use except as authorized in writing by the study sponsor
Behavioral Intervention Template Version: 11 January 2019

3 Objectives and Purpose

3.1 Primary Objective

Aim 1: To evaluate the effectiveness of Relay to reduce the frequency of opioid-related adverse events (any opioid-involved OD [fatal or nonfatal] or any other substance use-related ED visit), in the 12 months following the index visit, the primary outcome.

3.2 Secondary Objectives

Aim 2: To evaluate the impact of Relay on the following secondary outcomes: initiation of medication for opioid use disorder (MOUD); OD risk behaviors; time to next opioid-involved OD; ED visits for opioid OD, other substance use reason, and any cause; and self-reported opioid-involved OD.

Aim 3: To identify mediators (e.g., OD knowledge, support, experience of stigma, peer modeling) and moderators (e.g., substance use history, age, sex, housing status) of the effect of Relay.

Aim 4: To evaluate Relay's implementation by assessing fidelity to the program model and exploring barriers and facilitators to its delivery and sustainability through qualitative interviews with patients, Relay peer navigators, and ED providers.

4 Study Design and Endpoints

4.1 Description of Study Design

This 2-arm multi-center RCT compares site-directed care (SDC) to the Relay intervention among patients presenting to the ED with a nonfatal opioid-involved OD. When individuals present to the ED with opioid OD, ED staff call the Relay hotline. The hotline operator will notify the research team. A RA will meet the patient in the ED, assess study eligibility, complete informed consent, and randomize participants to the SDC vs. Relay arm. Participants in both arms will complete interviews with research staff at baseline and at 1, 3, and 6 months after enrollment, and will provide consent for viewing their information in administrative data sets. Administrative data provide measures for the primary 12-month outcome analysis. All appropriate and applicable permissions will be obtained from the holders of administrative data prior to their use for research. Qualitative interviews will provide additional information on implementation of Relay.

4.2 Study Endpoints

4.2.1 Primary Study Endpoints

The primary endpoint is the number of opioid-related adverse events in the 12 months following the index ED visit. Opioid-related adverse events include: any opioid-involved OD (fatal or nonfatal) or any other substance use-related ED visit.

4.2.2 Secondary Study Endpoints

Secondary endpoints include the impact of Relay on the following outcomes:

- Initiation of medication for opioid use disorder (MOUD)
- OD risk behaviors
- Time to next opioid-involved OD
- ED visits for any cause
- ED visits for opioid OD
- ED visits for other substance use reasons
- Self-reported opioid-involved OD

CONFIDENTIAL

We expect that Relay will be effective in increasing MOUD initiation because it is built on a foundation of prior work demonstrating that ED interventions by non-medical staff can effectively link patients to treatment. Measures of MOUD initiation will be gathered at each study visit. MOUD is defined as use of methadone, buprenorphine, or naltrexone that is prescribed by an office-based provider or provided by a treatment program as treatment for OUD. Initiation is defined as receiving MOUD within the 90 days following the index visit, for individuals who received no MOUD for at least 2 weeks prior to the index visit.³⁸ Though infrequent, if patients are initiated on MOUD during the index visit (in the ED or, if admitted from the ED, in the hospital), the first outpatient MOUD encounter post-discharge will be the measure of treatment initiation. We will include MOUD initiated in the ED in sensitivity analyses. Our primary analysis is limited to the individual's first episode of outpatient MOUD in the 90 days (3 months) following enrollment because this is the duration of contact with the Relay peer navigator and thus, for individuals in the Relay arm, is most attributable to the intervention. However, we will measure the total number of MOUD initiation episodes and time receiving MOUD for a full 6 months, to capture any continued intervention effect. Assessments at baseline and follow-up will collect data on MOUD in the past 90 days.

Relay offers motivational counseling as well as sustained peer navigation that provides support and access to services that could help individuals reduce their OD risk behaviors. As such, we expect to detect greater reductions in risk behaviors in the Relay compared to the SDC arm. We will measure OD risk behavior using questionnaires that were developed by a group of OD researchers based on knowledge of OD behavioral risk factors and used in 3 prior studies to capture OD risk behavior.^{49,50,52} These questions measure the frequency, in the past 3 months, at which individuals: 1) used >1 opioid; 2) used benzodiazepines, alcohol, or cocaine/stimulant within 2 hours of an opioid; 3) used alone or behind a locked door; 4) used in a place they had never used before; and 5) used more than usual amount. The total risk score is an aggregation of responses to the individual questions.

Time to next OD is measured using self-report. Frequency of ED visits for any cause (including visits that are not substance use-related) will be measured to assess whether there are differences in overall acute care use representing potentially negative health events. Additionally, we will examine frequency of ED visits for opioid OD and frequency of ED visits for other (non-OD) substance use reasons. These three ED visit secondary endpoints will be count outcomes using administrative data at 12 months and based on documentation of visit diagnosis (including primary and secondary diagnosis ICD codes, text diagnosis, and/or chief complaint). Self-reported opioid-involved OD is based on participant self-report in the 1-, 3- and 6-month follow-up visits and includes nonfatal ODs that did or did not result in an ED visit.

We will also examine multiple potential mediators and moderators of Relay program effectiveness as further described in later sections.

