7.1.1 Study Specific Procedures Overall

- Eligibility assessment and study consent
- Randomization to study arm
 - Relay intervention: peer navigator administered OEND, motivational counseling, referrals and support and linkage to services while in the ED and for up to 90 days post-discharge.
 - Site-directed Care: RA will ensure that participant receives, at a minimum, overdose prevention education consisting of OEND, treatment program list, and Relay informational handout.
- Administration of questionnaires for patient-reported outcomes, at baseline, 1-month, 3-months, and 6-months.
- Baseline exit survey documenting opioid-related services received by the participant in the ED.
- Collection of participant information (to allow linkage with administrative data)
- Collection of participant locator form information

CONFIDENTIAL

This material is the property of the NYU School of Medicine and NYU Langone Health. Do not disclose or use except as authorized in writing by the study sponsor

Behavioral Intervention Template Version: 11 January 2019

- Data extraction from administrative datasets including vital statistics / mortality data, DOHMH OD deaths data, and health services use data (which may include Regional Health Information System [RHIO], Statewide Planning and Research Cooperative System [SPARCS], Medicaid, and electronic medical record [EMR] data, as available)
- Semi-structured qualitative interviews with Relay participants, peer navigators, and ED staff.
- Assessment of study intervention adherence (Relay contact content checklists and assessment of DOHMH Relay program data)

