7.3 Study Schedule

7.3.1 Screening and Enrollment/Baseline

Screening/Enrollment/Baseline Visit (Visit 1, Day 0)

There is no separate screening visit for this study. Screening for study eligibility will occur during the same ED or hospital visit as the study enrollment / baseline visit. The only patients who are potentially eligible for the study and who will be screened by RAs are those for whom the ED staff has called the Relay program hotline. As part of existing protocols, ED staff at the study sites call the Relay program hotline for patients who have presented to the ED after a nonfatal opioid OD. ED staff are instructed to call the Relay hotline when a patient presents with nonfatal opioid OD, as determined by the treating clinician(s). The Relay hotline is operated by a HIPAA-compliant call center that provides 24-hour service, 365 days/year. It is used by all EDs participating in Relay, including the study sites. ED staff are instructed to call the Relay hotline as soon as they become aware of a patient presenting for nonfatal opioid OD, to help

CONFIDENTIAL

This material is the property of the NYU School of Medicine and NYU Langone Health. Do not disclose or use except as authorized in writing by the study sponsor

Behavioral Intervention Template Version: 11 January 2019

ensure that there is adequate time for both study procedures and (if randomized to the Relay arm) delivery of the Relay intervention.

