7.3.2 Intermediate Visits

Acceptable time windows are given for each study visit, but attempts will be made to conduct the visit as close as possible to the intended day (+/- 3 days when possible).

Visit 2 (Day 30 +14/-7) (*All participants, conducted by RA or PM)

- RA administers structured interview over the phone or in person (30-40 minutes).
- Study incentive payment added to ClinCard.

Visit 3 (Day 90 +30/-14) (*All participants, conducted by RA or PM)

- RA administers structured interview over the phone or in person (30-40 minutes).
- Study incentive payment added to ClinCard.

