7.3.3 Final Study Visit

Final Study Visit (Visit 4, Day 180 +30/-14) (*All participants, conducted by RA or PM)

- RA administers structured interview over the phone or in person (30-40 minutes).
- Participant is provided with final study incentive payment via ClinCard.
- Any questions about the study are answered and participant is given contact information for the study if needed.

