10.4.3 Analysis of the Secondary Endpoint(s)

Secondary outcome analysis. For secondary outcomes, we will use models similar to those for the primary outcome. Initiation of medication for opioid use disorder (MOUD) in the first 90 days will be evaluated using a logistic regression model with intervention arm as the primary predictor. In addition, we will explore multiple initiations of MOUD in the follow-up period using longitudinal generalized linear mixed models. These will use a logit link and incorporate random effects for participants to accommodate the correlation of repeated assessments. The OD risk behavior score will be evaluated using mixed effects models for continuous longitudinal data, incorporating random effects for participants as described. Item responses to the OD risk behavior questionnaire will be summed; higher scores indicate a higher number and/or frequency of risk behaviors. Time to first subsequent OD will be evaluated using Cox proportional hazards models. Frequency of ED visits for a) opioid OD, b) other substance use related reason, and c) any cause will be evaluated with Poisson regression models as described for the primary outcome. For all models, we will assess validity of assumptions regarding distributional characteristics of the outcomes and find suitable transformations if necessary. We will assess indicators of model fit and evaluate standard model diagnostics such as residual plots.

Qualitative interview analysis. One-on-one interviews will be conducted with approximately 12 patients,
CONFIDENTIAL

This material is the property of the NYU School of Medicine and NYU Langone Health. Do not disclose or use except as authorized in writing by the study sponsor

Behavioral Intervention Template Version: 11 January 2019

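### The overdose-risk score looks back 3 months at a visit about 30 days after randomisation, so a treatment effect pooled over months 1, 3 and 6 would be attenuated

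*Combined protocol and SAP*

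**What the plan says.** - **Recall period.** Section 4.2.2 says of the OD-risk items: "These questions measure the frequency, in the past 3 months, at which individuals" did each of five listed things. It gives no other recall period for follow-up visits.
- **Schedule.** Section 7.1.1 lists "Administration of questionnaires for patient-reported outcomes, at baseline, 1-month, 3-months, and 6-months". Day 0 is set in section 7.3.1 ("Screening/Enrollment/Baseline Visit (Visit 1, Day 0"); randomisation and the first Relay contact belong to that visit. Sections 7.3.2 and 7.3.3 then set "Visit 2 (Day 30 +14/-7"), "Visit 3 (Day 90 +30/-14") and "Final Study Visit (Visit 4, Day 180 +30/-14").
- **Analysis.** Section 10.4.3: "The OD risk behavior score will be evaluated using mixed effects models for continuous longitudinal data", with random effects for participants. It names no main visit, no visit weights and no arm-by-visit term.
- **Medication for opioid use disorder (MOUD).** Section 4.2.2 adds: "Assessments at baseline and follow-up will collect data on MOUD in the past 90 days". The MOUD endpoint itself is tied to the 90 days after the index visit, and section 10.4.3 tests it in one logistic model.

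**The concern.** A 3-month recall suits visits that are 3 months apart. At a visit held one month after randomisation, most of the period asked about was over before either arm received anything. The month-1 score is then largely a second measurement of baseline: at Day 30 its window runs from Day -60 to Day 30 and shares 60 days with the baseline window. If it counts as a full post-treatment measurement, it pulls the estimated effect toward zero.

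Section 4.2.2 expects larger reductions in risk behaviour in the Relay arm, and attenuation works against showing that. In a visit-by-visit display it could also make an immediate effect look delayed.

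**Working it through.** The documents give no power or effect size for the OD-risk score (section 10.5 only expects power to be adequate for secondary outcomes), so there is no stated figure to reproduce.

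**Inputs from the protocol.** Recall L = 3 months, taken as 90 days (section 4.2.2). Visit days: month 1, Day 30 (23 to 44); month 3, Day 90 (76 to 120); month 6, Day 180 (166 to 210) (sections 7.3.2 and 7.3.3).

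**Step 1. Share of the window before randomisation** = max(0, L − t)/L for a visit on day t.

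| Visit | Day | Share before Day 0 |
|---|---|---|
| Month 1 | 23 | 67/90 = 74% |
| Month 1 | 30 | 60/90 = 67% |
| Month 1 | 44 | 46/90 = 51% |
| Month 3 | 76 | 14/90 = 16% |
| Month 3 | 90 or later | 0% |
| Month 6 | 166 to 210 | 0% |

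Reading 3 months as 91.3 days changes the Day 30 figure only to 67.1%.

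**Step 2. Effect retained.** Assumptions: a constant effect from Day 0, none before it, and recall that weights all days equally. Each visit then keeps the fraction min(1, t/90) of the true effect. Month 1 keeps 30/90 = 33% (23/90 = 26% to 44/90 = 49%). For a common effect with equal visit weights:

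- Days 30, 90, 180: (0.333 + 1 + 1)/3 = 0.78
- Lowest, Days 23 and 76: (0.256 + 0.844 + 1)/3 = 0.70
- Highest, Day 44 with month 3 on Day 90 or later: (0.489 + 1 + 1)/3 = 0.83

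**Step 3. Power, as illustration only.** Suppose the average of months 3 and 6 alone has 80% power at two-sided 0.05, so its expected z is 1.960 + 0.842 = 2.802. Assume equal correlation r between visits, equal variances and no baseline adjustment. Adding month 1 at Day 30 multiplies z by

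[0.778/√((1 + 2r)/3)] / [1/√((1 + r)/2)],

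which is 0.86, 0.82 and 0.80 for r = 0.3, 0.5 and 0.7. Power = Φ(2.802 × ratio − 1.960), or about 67%, 64% and 61%. The values of r are assumed. Under these assumptions the extra visit costs power, but the amount depends on the model.

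**Step 4. What month 1 adds.** With month 3 on Day 90, that visit's window is exactly Days 0 to 90, so the first 30 days are already in the month-3 score. Month 1 supplies post-randomisation days that month 3 misses only when month 3 is late: on Day 120 its window starts at Day 30.

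**The case against.** **The form has not been seen.** The follow-up questionnaires (Attachment J) are not in the text. Section 4.2.2 describes an instrument used in earlier studies and does not state its recall visit by visit. Other follow-up items do ask about the time since the last visit: incarceration in section 5.3.1 and Relay services in section 6.1.2. This stands as a limit. An unchanged recall is the natural reading, because the protocol states one period and no exception, but it is an inference about the form.

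**The model is not fixed.** Section 10.4.3 does not commit to a common effect. With arm-by-visit terms, the dilution stays at month 1, with a little at an early month 3. Section 10.1 calls the approaches preliminary and leaves the detailed plan until before outcome analysis. This also stands: the attenuation of the overall estimate is conditional. It is equally why the contrast should be named now.

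**The power figures depend on the model.** Month 1 shares 60 of its 90 days with baseline, so baseline adjustment and the covariance structure change how much weight it receives. The figures of 61% to 67% should not be quoted as the trial's power loss.

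**A reader might infer that the MOUD endpoint is diluted too.** The documents do not support that. Initiation means receipt within 90 days after the index visit, limited in the main analysis to the first outpatient episode and tested once over that period. There is no month-1 MOUD contrast, and a 90-day recall on Day 90 covers exactly the endpoint period. Counting pre-index use as initiation, or counting episodes twice where windows overlap, would require that start dates go unrecorded. The text neither confirms nor excludes this, and MOUD in the 90 days before baseline is asked about separately.

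**A reader might also infer a 44-day hole in recall** (210 − 90 − 76 = 44). It needs month 3 at its earliest limit and month 6 at its latest. At the nominal days the gap is zero, and at the ±3 days that staff aim for it is at most 6 days.

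**Conclusion.** The point holds for the OD-risk score. On the stated recall and schedule, 67% of the month-1 window precedes randomisation (51% to 74%). A common effect over months 1, 3 and 6 would keep about 78% of the true effect (70% to 83%). This rests on an unchanged recall at month 1, a constant effect from Day 0, evenly weighted recall and equal visit weights.

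The direction is toward no difference. Randomisation balances the pre-index period between arms, so nothing here favours either arm. The month-6 score is unaffected. Because the contrast is left open, this is a cheap improvement to the plan and not a demonstrated error in a fixed analysis.

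**What to change.** In section 10.4.3, define the OD-risk treatment contrast on the 3- and 6-month scores, for example as the average of those two arm differences from a model with arm-by-visit terms. Report month 1 descriptively or as a separate visit-specific estimate, with a note that most of its recall period precedes randomisation.

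The cost is one sentence and one repeated measure in the contrast. Section 10.1 leaves room for this before outcome analysis, and it works even if the data are already collected.

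Asking the month-1 items about the time since the ED visit would also remove the overlap. It costs more: the score would cover a different length of time from the other visits and need scaling, and the 3-month recall stands in the protocol body (section 4.2.2), so that text would have to change as well. The allowance in section 19 for changing attachments does not by itself cover this, and section 13.2 requires IRB approval of protocol amendments.

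For MOUD, confirm that the follow-up items record start dates and add them if they do not. Pre-index use inside the month-1 look-back then cannot be counted as initiation, and overlapping windows cannot be counted twice.

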5.3.1 Inclusion of Patients who become Prisoners during the Study

It is possible that during the course of the study, some individuals in our study population may become considered prisoners. Our study enrolls a population with high rates of criminal justice involvement as a consequence of their opioid use. Incarceration is a major risk factor for opioid-related overdose, and data on overdose and other substance-related adverse among this population is important for evaluating the effectiveness of the Relay intervention in our population of interest.

Though the study will not enroll people who are considered prisoners at the time of enrollment, participants could potentially become prisoners over the course of their participation in the study. We will seek OHRP approval to ascertain follow-up data using administrative data sources only from these participants during the periods in which they are considered prisoners. We will not attempt to complete follow-up surveys with prisoners who are currently detained in a residential facility, due to a lack of ability to contact them in a secure, HIPAA-compliant manner. We do plan to use hospital administrative data that may include dates during which these individuals are considered prisoners. This data will be gathered through data abstraction from a variety of administrative health databases, as described in section 14.1. As collection of this information does not involve directly contacting the participants, we do not expect that the use of this administrative data constitutes an increased risk to these individuals.

We will not be notified when a study participant becomes considered a prisoner during the course of the study. We do include questions regarding whether a person has been incarcerated since the previous study visit in our follow-up surveys. For follow-up study visits that are conducted by phone, research staff will confirm that the participant has privacy and is not a prisoner prior to administering research assessments.

If an individual is considered a prisoner past the end of the study, we will not conduct any additional follow-up, but will use the hospital administrative data from the time that they were a study participant. If an individual is considered a prisoner at one point in the study, and later in the study is no longer considered a prisoner, we will attempt to conduct all follow-up assessments as scheduled.

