5.7.2 Handling of Participant Withdrawals or Termination

If participants request to withdraw from the study, they will be asked whether the data already collected from them can still be used. Participants will be asked to provide their request for study withdrawal in writing, sent to the study PI. Participants may choose not to complete individual follow-up interviews without actually formally withdrawing from the study; in such cases investigators will affirm with participants that we can still access their health care data for measurement of the study outcomes. The primary outcome measures use administrative data, which will be available for all individuals who enroll in the study, even if they are lost to follow-up, unless they have withdrawn permission for us to use their data. Participants who withdraw or are terminated from the study may still receive continued services from the DOHMH Relay program if they desire them.

If a participant is terminated from the study by the investigators, the participant will be informed in writing via a letter mailed to their primary address. Due to confidentiality concerns, details of the reason for termination will only be provided to the participant directly by phone.

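### Time to next opioid-involved overdose has self-report as its only source, so a fatal next overdose cannot be an event and an ED-recorded one counts only if a later interview captures it

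*Combined protocol and SAP*

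**What the plan says.** Section 4.2.2 lists the endpoint as "Time to next opioid-involved OD" and gives its source in one sentence: "Time to next OD is measured using self-report". The same section describes a separate secondary endpoint, self-reported opioid-involved OD, which comes from the 1-, 3- and 6-month interviews and "includes nonfatal ODs that did or did not result in an ED visit".

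Section 10.4.3 gives the analysis: "Time to first subsequent OD will be evaluated using Cox proportional hazards models". It states no horizon, event date or rule for death for this endpoint.

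In Section 4.2.1 the primary endpoint uses the same term with an explicit scope: "any opioid-involved OD (fatal or nonfatal", together with other substance use-related ED visits. Section 10.4.2 takes fatal ODs from the city health department's (DOHMH) overdose-death database and ED visits from administrative data over 12 months. Section 5.7.2 says of the administrative data behind the primary outcome that they are data "which will be available for all individuals who enroll in the study, even if they are lost to follow-up", except where a participant has withdrawn permission. Section 4.2.3 adds vital records for the death outcomes.

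**The concern.** The endpoint's name suggests the next opioid OD of any kind. Its only named source can deliver nonfatal ODs that a living participant reports at an interview, and nothing else. Fatal OD is the event that Relay most needs to prevent, yet here it would remove a participant from the risk set without counting against either arm.

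Two things are at stake. First, one participant's fatal OD would count as an event in the primary outcome and as no event in an analysis that readers will take to be about the same kind of OD. Second, if Relay makes ODs less often fatal, ODs survived in the Relay arm can become events while the corresponding deaths under site-directed care are censored. Section 6.1 describes naloxone provision and discussion of how it protects against fatal OD, so such an effect is one the programme intends.

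**Working it through.** There is no stated figure to reproduce. The plan gives no event count, hazard ratio or power for this endpoint; Section 10.5 says only that the event is expected not to be rare. The check is therefore on the text.

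**Step 1: sources, endpoint by endpoint.**
- Primary outcome (10.4.2): death database, administrative data, and self-report for other nonfatal ODs.
- Three ED-visit counts (4.2.2): administrative data at 12 months.
- Self-reported OD (4.2.2): interviews at 1, 3 and 6 months, nonfatal events.
- Death outcomes (4.2.3): vital records and DOHMH reports.
- Time to next opioid-involved OD (4.2.2, 10.4.3): self-report. The other places that mention this endpoint (Protocol Summary, Sections 3.2 and 10.5) add no source.

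**Step 2: each kind of next OD under the rule as written.**
- Fatal: never an event here; held in the death data.
- Nonfatal, seen in an ED, later interview captures it: an event.
- Nonfatal, seen in an ED, no later interview captures it: missed here; available in the administrative data.
- Nonfatal, not seen in an ED, reported: an event.
- Nonfatal, not seen in an ED, not reported: missed here, and no source named in Step 1 recovers it.

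So two of the five kinds are lost to this endpoint although the trial collects them.

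**Step 3: direction of the effect of censoring fatal ODs.** Suppose, for illustration, that both arms have the same opioid-OD hazard λ(t), that reporting is complete, and that a share f of ODs is fatal, with f_R in Relay and f_S in site-directed care.
- Hazard ratio for any opioid OD = λ(t)/λ(t) = 1.
- Hazard ratio for nonfatal OD = λ(t)(1 − f_R) / [λ(t)(1 − f_S)] = (1 − f_R)/(1 − f_S).
- If f_R < f_S, the second ratio exceeds 1: Relay looks worse although the OD rates are equal. Its upper limit, at f_R = 0, is 1/(1 − f_S). If f_R = f_S, the ratio is 1 and nothing is distorted.

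**Step 4: size.** The documents give no value for f_S or f_R and no interview completion by arm. The 10% one-year mortality in Section 2.1 is for death from any cause in another population, so it is not an OD fatality share. The number of participants affected is unknown. What can be counted is reach: Section 4.2.2 lists seven secondary endpoints, and this is one of them.

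**The case against.** The strongest reply is that the design is coherent as it stands. The fatal-or-nonfatal wording in Section 4.2.1 qualifies the primary endpoint and need not define the term everywhere. ED visits for opioid OD and opioid-OD deaths are listed as outcomes of their own, so a nonfatal, self-reported time-to-event endpoint would complement them. That stands as far as it goes: the target is legitimate. But the plan never says that it is the target, and the endpoint's name points to something wider.

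Section 8.1 might seem to answer the point, because it lists opioid-involved OD, fatal and nonfatal, as captured from questionnaires and administrative data. That list serves safety reporting and does not redefine this endpoint.

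Section 10.1 defers a detailed analysis plan. Section 10.4.3 also says that secondary models resemble the primary one, where follow-up time is adjusted for death or withdrawal; censoring at death is the natural Cox counterpart. The follow-up questionnaires (Attachment J, not shown) may collect OD dates. These replies weigh on horizon, dating and death handling, which are missing detail and may yet be settled. They do not change the source that Section 4.2.2 states.

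Some events are recovered. Staff may interview participants who return to an ED (Sections 5.4.1 and 7.3.5). A reader might also infer that ODs in detained participants are lost altogether, since the plan says: "We will not attempt to complete follow-up surveys with prisoners who are currently detained in a residential facility". The same section says that for those later released "we will attempt to conduct all follow-up assessments as scheduled", so that loss is partial and its size unknown. Neither route recovers a fatal OD.

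**Conclusion.** The point holds on the text and is minor to moderate. A stated rule, not only a missing detail, keeps fatal next ODs out of the event definition and loses ED-recorded ODs that no later interview captures, while the trial already holds better data on both. The possible bias against Relay rests on one assumption, that Relay lowers the share of ODs that are fatal; without it, Step 3 gives no distortion.

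Three stronger readings are tempting and are not supported.
- That the trial loses its evidence on fatal or ED-treated OD. It does not: these are analysed in the primary outcome, the ED-visit counts and the death outcomes.
- That the visit windows measure the defect. The last interview may fall from day 180 − 14 = 166 to day 180 + 30 = 210, which leaves 365 − 210 = 155 to 365 − 166 = 199 days of the year (42% to 55%) outside self-report. This reflects the roughly 6-month horizon that the schedule implies. A full-source analysis stopped at day 180 would also leave 185 of 365 days (51%) outside, and staggered censoring is routine in a Cox model.
- That the hazard ratio is biased against Relay. The documents show only that it could be.

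**What to change.** Change Sections 4.2.2 and 10.4.3 so that the event is the earliest of:
- fatal opioid OD (DOHMH or vital records);
- an ED visit for opioid OD (administrative data);
- self-reported opioid-involved OD.

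Date the event by the record where one exists. Censor at death not due to opioid OD, at withdrawal of data permission, or at the stated horizon. State the horizon and the dating of self-reported events in the detailed plan, after checking whether Attachment J already collects dates.

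ODs that do not reach an ED are unseen after the last completed interview, so also report:
- (a) fatal and ED-recorded ODs only. This does not depend on interview completion and can run to 12 months. It is subject to the completeness of the administrative sources, which Section 14.1 does not take for granted, and to the death database covering New York City.
- (b) self-report censored at the last completed interview, labelled as nonfatal, self-reported OD, with interview completion shown by arm.

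The cost is small: endpoint wording, a merge of dates from sources already planned for the primary outcome, and a check that the abstraction tool (Attachment P, not shown) records visit dates. The remaining weakness is uneven ascertainment of non-ED ODs in the combined analysis, which treats time after the last interview as free of them. Analyses (a) and (b) are there to show whether that matters.
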